5.2. Endpoints

5.2.1. Primary Endpoint

Respiratory depression is a clinical diagnosis made after reviewing monitoring data in conjunction with the clinical data and consistent with accepted pathophysiologic mechanisms.

Version 3.0, 29 Nov 2016

PRODIGY CIP

The primary endpoint used to derive the score will be the incidence of RD episodes captured by continuous capnography and pulse oximetry measurements recorded on the Capnostream device memory data in conjunction with the clinical data as reported by the investigator.

RD determination will be validated by an independent Clinical Event Committee (CEC). The CEC will use both clinical data and monitor parameters specificed below as a guideline; if determination of an RD episode is clinically appropriate but outside of the guidelines a rationale will be provided.

Data suggestive of an RD episodes include any of the following:

- etCO₂ \leq 15 or \geq 60 mmHg for \geq 3 minutes.
- or
 - RR ≤ 5 breaths for ≥ 3 minutes.
- or
 - SpO₂ \leq 85% for \geq 3 minutes.
- or
 - Apnea episode lasting > 30 seconds.
- or
- Any respiratory Opioid-Related Adverse Event (rORADE).

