5.2.2. Secondary Endpoint(s)

- 1. RD risk subjects versus no-risk subjects will be compared in terms of:
 - Incidence of AE's and actions taken.
 - Healthcare resource utilization (including hospital length of stay, 30 days readmission rate and primary diagnosis upon readmission).
 - Subject mortality at 30 days.
- 2. The predictive value (sensitivity, specificity, etc.) of etCO2, RR, SpO2, and IPI will be correlated with the occurrence of RD and ORADE.
- 3. Cost associated with events and actions taken will be estimated retrospectively using standard cost data from different countries.

6. Study Design

PRODIGY is a prospective, post-market interventional, multi-center, international cohort study.

A derivation cohort will be used to derive the risk assessment tool. An internal validation cohort will be used for evaluating the prognostic value of the score for the prediction of RD. Capnography and pulse oximetry monitoring device data will be collected as well as clinical data related to respiratory depression. Subjects will be monitored per standard of care. Enrollment at any single site will be limited to 20% (approximately 330 subjects) to ensure poolability of the data across sites and reduce potential bias. Additional methods incorporated to minimize potential bias include the following:

- Systematic identification of potential subjects via screening
- Both surgical and non-surgical candidates are eligible as event rates may vary
- Adjudication of RD events by an independent review committee
- Diverse geographical site representation to account for difference in practice

Version 3.0, 29 Nov 2016

PRODIGY CIP

- Standard procedures and data collection requirements with a common electronic database for all sites
- Provision of product for all study subjects

Foreseeable factors that may compromise the outcome of the study include lack of enrollment or the lack of respiratory depression events.

Approximately 1650 subjects will be enrolled in up to 16 centers from the United States (US), Europe and Asia. Geographic distribution of sites is anticipated as 8 sites (50%) in the US, 5 (30%) in Europe and 3 (20%) in Asia. Additional locations may be added during the course of the study.

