9.10. Recording Data

The investigator will clearly mark the clinical records to indicate that the subject is enrolled in this clinical study. Subject's medical record will be used as source documents. Worksheets could serve as source documentation in particular cases if a data field is not in the subject's medical record.

Capnostream device memory data will be the source for the number and duration of RD episodes. RD data reports will be derived from the device memory data. The reports are used for primary endpoint validation from the Clinical Event Committee.

The investigator must ensure accuracy, completeness and timeliness of the data reported in the eCRFs and in all other required reports. Data reported on the eCRFs which are derived from source documents, such as patient medical records, must be consistent with the source documents or the discrepancies need to be justified in a documented rationale, signed and dated by the (principal) investigator, to be filed in the subject file. All baseline and medical history data must be derived from source documents.

Only authorized persons can complete eCRFs. Training will be provided to site personnel on the use of data collection tools. CRFs shall be electronically signed by investigators (physician) or by authorized site staff as specified on the Delegated Tasks List. Final version of eCRFs will be provided to the investigation sites when the investigational site has been declared ready for the study.

It is expected that eCRF will be completed within 15 days from the performed visit or as soon as source documents are available, except for Serious Adverse Events that require immediate reporting (see Table 3) and for Protocol Deviation requiring pre-approval. A delayed completion of the eCRF will not be considered a Protocol Deviation.

Sponsor study personnel will review all collected data and create data queries for missing data that impacts data analysis. Queries will be sent to the investigator or appropriate support staff for resolution.

Data reported on the eCRFs that are derived from source documents must be consistent with the source documents. Where copies of the original source document as well as print outs of original electronic source documents are retained, these shall be signed and dated by a member of the investigation site team with a statement that it is a true reproduction of the original source document.

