12.1. Clinical Event Committee

The Clinical Event Committeee (CEC) is an independent committee of experts not participating in the clinical study that provides adjudication of study specific endpoints and/or events utilizing study-specific or consensus definitions available in the field. The committee will consist of a minimum of three (3) non-Medtronic experts experienced in evaluating respiratory compromise, respiratory depression, and interpreting continuous monitor data.

The CEC roles are to:

- Review AE's to classify the event as respiratory or non-respiratory.
- Review AE's to determine the relatedness (including device or opioid therapy).
- Review Respiratory Depression (RD) episodes and classify them as such based on the primary endpoint definition of RD.

Composition, roles and responsibilities of CEC will be described in a separate charter.

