7.10.2.2 Secondary endpoint#2

The secondary objective#2 will characterize the predictive values of etCO₂, RR, SpO₂ and the IPI⁵ in predicting rORADE. To evaluate the predictive values of the Capnostream monitoring parameters for rORADE, the Sensitivity, Specificity, PPV and NPV will be calculated. rORADE events will be considered the Gold standard and the CS20p monitoring parameters as the measurement to be tested. The population used for this endpoint is PRDPS adjudicated as RD. All Clinical Events occurring during not monitored period will be reported but excluded from the table below. For each RD adjudicated by the CEC, the Capnostream monitoring will be checked if any of the parameter meets at least once the thresholds (RR \leq 6 breaths for \geq 3 minutes, SpO₂ \leq 85% for \geq 3 minutes, EtCO₂ \geq 60 mmHg for \geq 3 minutes or IPI < 3,4,5,6). The table below shows the distribution of the true and false positive and negative for each monitored parameter:

Test		Gold Standard		
Monitoring Parameter		ORADEs/RDs		
RR ≤ 5 breaths for ≥ 3 minutes		YES	NO	Tot
	YES	TP	FP	TP+FP
	NO	FN	TN	FN+TN
	Tot	TP+FN	FP+TN	N
Monitoring Parameter		ORADEs/RDs		
SpO2 ≤ 85% for ≥ 3 minutes		YES	NO	Tot
	YES	TP	FP	TP+FP
	NO	FN	TN	FN+TN
	Tot	TP+FN	FP+TN	N
Monitoring Parameter		ORADEs/RDs		
etCO2 ≤ 15 or ≥ 60 mmHg for ≥ 3 minutes		YES	NO	Tot
	YES	TP	FP	TP+FP
	NO	FN	TN	FN+TN
	Tot	TP+FN	FP+TN	N
Monitoring Parameter		ORADEs/RDs		
IPI <3		YES	NO	Tot
	YES	TP	FP	TP+FP
	NO	FN	TN	FN+TN
	Tot	TP+FN	FP+TN	N
IPI <4		YES	NO	Tot
	YES	TP	FP	TP+FP
	NO	FN	TN	FN+TN
	Tot	TP+FN	FP+TN	N
IPI <5		YES	NO	Tot
	YES	TP	FP	TP+FP
	NO	FN	TN	FN+TN
	Tot	TP+FN	FP+TN	N
IPI <6		YES	NO	Tot
	YES	TP	FP	TP+FP
	NO	FN	TN	FN+TN
	Tot	TP+FN	FP+TN	N
Monitoring Parameter		ORADEs/RDs		
Any Monitoring Parameter RR ≤ 6 breaths for ≥ 3 min or SpO2 ≤ 85% for ≥ 3 min or EtCO2 ≥ 60 mmHg for ≥ 3 min or IPI < 3,4,5,6		YES	NO	Tot
	YES	TP	FP	TP+FP
	NO	FN	TN	FN+TN
	Tot	TP+FN	FP+TN	N

Where:

- N will be all RDs adjudicated by the CEC.
- TP= true positive are all rORADEs and parameter over/below the threshold.
- FN= false negative are all rORADEs but no parameter over/below the threshold.
- FP= false positive are all no rORADE but parameter over/below the threshold.
- TN=true negative are all no ORADEs and no parameter over/below the threshold.

Measure of the accuracy will be:

- Sensitivity: $\{TP/(TP+FN)\}$,
- Specificity: $\{TN/(FP+TN)\}$,
- Positive predictive value: $\{TP/(TP+FP)\}$,

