9.3 Detection Tool

The Detection Tool analyzes each patient's monitoring using an algorithm based on the device episodes thresholds as stated in the primary endpoint. The Detection Tool provides for each patient multiple Episodes. Since there could be multiple episodes in a short time period around each Episode, the Detection Tool is set to aggregate episodes with at most 30 minutes time difference between them in one file. In addition the episodes file consists of time window of 30 min before and after the first and last episode.

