9.4 Priority List

The CEC will stop the adjudications at the first RD for each patient, while they will adjudicate all Clinical Events. In order to optimize CEC time the following priority list will be used to prioritize some Episode-File to be review first:

Priority 1: all clinical events with/without any episode from device data. In case multiple Clinical events per patient the CEC will review them using the time of occurrence, from first clinical event to the last.

Priority 2: Multiple episodes involving at least two parameters among SpO₂, EtCO₂, RR and Apnea. In case of multiple Episode-Files with this priority the CEC will review first the Episode-Files with the higher number of Episodes within the Episode-Files.

Priority 3: Multiple Episodes of the same parameter. In case of multiple Episode-Files with this priority the CEC will review using this order: SpO₂, EtCO₂, RR and Apnea

Priority 4: Any overnight Episodes of the same parameter. In case of multiple Episode-Files with this priority the CEC will review using this order: SpO₂, EtCO₂, RR and Apnea

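### Secondary endpoint 2 keeps RD as an accuracy target although RD is built from the tested monitor parameters, and the rORADE reference is not stated to be called blind to the trace

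*Protocol*

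**What the plan says.** **The target.** Protocol 5.1.2 and SAP 4.2.2 name both RD and ORADE as outcomes to be predicted from etCO2, RR, SpO2 and IPI. Protocol 5.2.2 repeats this: "The predictive value (sensitivity, specificity, etc.) of etCO2, RR, SpO2, and IPI will be correlated with the occurrence of RD and ORADE".

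**How RD is made.** Protocol 5.2.1 lists limits on etCO2, RR and SpO2, an apnea criterion and any rORADE as data suggestive of RD. It adds that "The CEC will use both clinical data and monitor parameters specificed below as a guideline"; the committee may depart from the list if it gives a rationale. Candidate episodes come from a Detection Tool that runs "an algorithm based on the device episodes thresholds as stated in the primary endpoint" (SAP 9.3). Protocol 9.10 says of the device-derived RD reports: "The reports are used for primary endpoint validation from the Clinical Event Committee". Protocol 7.1.1 states that IPI is calculated from etCO2, RR, SpO2 and pulse rate only.

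**What the SAP does.** SAP 7.10.2.2 narrows the analysis: "rORADE events will be considered the Gold standard and the CS20p monitoring parameters as the measurement to be tested". It defines all four cells by rORADE status and sets N to the RDs that the CEC has adjudicated. Yet each two-by-two table is headed with ORADEs and RDs together, and the title of Table 27 names both.

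**How rORADE is made.** Among the CEC's tasks in protocol 12.1 is "Review AE's to classify the event as respiratory or non-respiratory"; another is to judge relatedness to opioid therapy. In the SAP 9.4 review order, clinical events come first: "Priority 1: all clinical events with/without any episode from device data". The detailed CEC process is left to a separate charter.

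**The concern.** An accuracy study needs a reference standard that does not contain the test. Here the single-parameter rows in SAP 7.10.2.2 (RR ≤5, SpO2 ≤85%, etCO2 ≤15 or ≥60, each for at least 3 minutes) are the same limits that trigger an RD candidate and guide its adjudication. Accuracy against RD then partly measures the monitor's agreement with itself.

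For rORADE the link is indirect. The committee that decides whether an adverse event is respiratory and opioid-related also reviews device data. If the trace is open at that moment, an event with a quiet trace may be less likely to be called an rORADE, and a false negative would drop out of the table.

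At stake is whether Table 27 can be read as evidence that the monitor parameters predict clinical events. The primary risk score is not affected, because it uses baseline predictors (SAP 7.10.1.1).

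**Working it through.** **1. The plan's own figure.** The documents give no expected accuracy, precision or sample size for endpoint 2. The nearest figures are the threshold incidences in protocol 13.1: RR 1.4%, SpO2 10%, etCO2 1%, with a stated union of 12%. Assuming independence:

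- 1 − (1 − 0.014)(1 − 0.10)(1 − 0.01) = 1 − 0.8785 = 12.15%, which rounds to the stated 12%.

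**2. RD as the target.** Suppose the CEC follows the thresholds.

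- A crossing without RD cannot occur, so FP = 0 for every single threshold. Specificity = TN/(TN + 0) = 100% and PPV = TP/(TP + 0) = 100%, whatever the patients are like.
- Sensitivity is the parameter's share of RDs: SpO2 0.10/0.1215 = 82%; RR 0.014/0.1215 = 12%; etCO2 0.01/0.1215 = 8%.

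These shares are illustrative. Protocol 13.1 uses RR ≤8 and only the upper etCO2 limit, so the inputs are not the tested thresholds, and apnea-only or clinical-only RDs would lower the shares. Where the CEC departs from its guideline, the 100% values fall, but the circularity remains in part. IPI is built from the same signals plus pulse rate, so it is exposed too, without an exact 100%.

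In the SAP table every row is an adjudicated RD. With RD as the target, the column for no RD is empty and specificity is 0/0. The RD label in those headings therefore cannot be given a meaningful accuracy.

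**3. rORADE as the target.** The documents give no rORADE counts. Assume TP = 12 and FN = 8, so true sensitivity is 12/20 = 60%. Let a fraction f of the false negatives be lost because a quiet trace leads the CEC not to call them rORADE. Sensitivity = 12/(12 + 8(1 − f)):

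- f = 0.10: 12/19.2 = 62.5%
- f = 0.25: 12/18 = 66.7%

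PPV = TP/(TP + FP) contains no FN, so it does not move.

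**4. Specificity and NPV for rORADE.** The SAP table holds only adjudicated RDs, most of which would have been found because a threshold was crossed. With the incidences above, and no apnea-only RDs, SpO2 specificity would be about 1 − 0.82 = 18% among non-rORADE RDs, against 1 − 0.10 = 90% in all patients. That row selection pushes specificity and NPV down, against any upward pull from an unblinded reference.

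**The case against.** The strongest reply is that RD is already superseded. SAP 7.10.2.2 defines every cell by rORADE, so what is left is objective wording and table labels. That is largely right for the cell definitions. It does not settle the matter, because the protocol and SAP objectives, the headings and Table 27 still promise accuracy against RD, and a reader of the report could be given it.

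The second reply is that nothing shows the trace being used to classify adverse events. The sentence on using monitor parameters concerns RD determination, protocol 12.1 lists adverse-event review and RD review as separate tasks, and SAP 9.4 sets only a review order. The charter is not among the documents reviewed and may already fix the sequence. In addition, site staff work with the monitor screen blinded and its alarms silenced (protocol 9.6), and the site's adverse-event record already covers respiratory nature and opioid relatedness (protocol 11.2). All of this stands. It protects the first report but not the CEC's own call, so the rORADE part is a risk only.

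A reader might also infer that PPV would rise because threshold-positive RDs are upgraded to rORADE. The documents do not support that in general: an asymptomatic RD with no action taken is not an adverse event (protocol section 11 and Appendix A), so the CEC has no adverse-event call on it to change. PPV could change only for false positives that already carry a reviewed adverse event, and their number is unknown.

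Finally, withholding physiology from the relatedness call may make that call less well informed. This is a real trade-off.

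**Conclusion.** The point holds for RD. Accuracy of etCO2, RR, SpO2 and IPI against RD is circular. If the CEC follows its guideline, specificity and PPV of each single threshold are 100% by construction, and sensitivity is only a share of RDs.

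For rORADE it is an open risk. It rests on two facts, namely that one committee does both tasks and that neither document states an order, and on the assumption that the trace is seen before the call. The likely effect is on sensitivity: 62.5–66.7% instead of 60% with the assumed counts and a loss of 10–25% of false negatives.

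It would be tempting to conclude that all predictive values are inflated. The documents do not support that. Single-parameter sensitivity against RD can be low, PPV against rORADE need not move, and the net direction for specificity and NPV cannot be stated while the table contains only adjudicated RDs. The matter concerns one secondary endpoint and should be corrected in the wording.

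**What to change.** 1. In protocol 5.1.2 and 5.2.2, SAP 4.2.2, the table headings in SAP 7.10.2.2 and Table 27, remove RD as a target of predictive value and keep rORADE. For RD, report only the share of confirmed RDs that meet each threshold. Protocol 13.4, which speaks of predicting episodes without saying which, should be aligned.
2. In protocol 12.1 and SAP 7.10.1 and 9.4, state that the CEC records the respiratory and opioid-related call on each adverse event from the clinical record and locks it before the Episode-File is opened. RD adjudication with device data then proceeds as planned. If the charter already requires this order, cite it.

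While editing SAP 7.10.2.2, reconcile its thresholds: the text and the combined row use RR ≤6 and only the upper etCO2 limit, whereas the single-parameter tables use RR ≤5 and both etCO2 limits.

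The cost is a small change to the order of items on the CEC form, and wording; no extra reader or patient data are needed. Adverse-event calls would be made without the trace, and reported sensitivity would probably be lower. The change does not cure the RD-only denominator, which still limits what specificity and NPV can mean.

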6.1. Duration

At least 20 subjects per month are expected to be enrolled at each participating center. Each participating site may involve one or more wards, based on its distribution of subjects receiving opioid therapy.

The study is expected to last approximately 10-13 (10-12 months of enrollment plus 30 days from the last enrolled subject). Not all the participating centers will be active at the moment of enrollment start.

Each subject will be followed-up for a maximum period of 30 days.

6.2. Rationale

The need of a simple tool to stratify patients at risk for developing RD has been identified to understand individuals that may benefit from capnographic monitoring. The chosen study design was based on predictive models that are often used to predict the probability that a subject with a given set of risk factors will experience an outcome. However the predictive ability of the model should be evaluated before any use in clinical practice. This is known as the validation step. The standard regression method used for analysis could accurately predict outcomes for subjects in the dataset used to develop the model, but may often perform less well in a new subject group. This difference is due to the random variation present in the development dataset. Therefore, the need to validate the risk score in another validating set of subjects has been incorporated.

This study will also collect data on a high number of subjects monitored by capnographic monitoring, thus allowing understanding of the real incidence of RD, especially in non-surgical subjects for which there are no data in the literature.

7. Product Description

7.1. General

The Capnostream monitoring system includes a capnograph/pulse oximeter monitor, sampling line for end tidal carbon dioxide (etCO₂), and pulse oximetry sensor for measuring the peripheral oxygen saturation of arterial hemoglobin (SpO_2).

All devices used in this study are commercially available (cleared by FDA, MHLW/PMDA and CE-Marked) and used within intended use in the participating geographies. The Instruction for Use (IFU) manual is provided with the product in the local language.

Table 1 provides a list of commercially available product that may be be used in the study.

Version 3.0, 29 Nov 2016

PRODIGY CIP

COVMOPO0560

Model or Version	Product		
CS08651-02 PM35MN	Capnostream Monitor • Capnostream [™] 20p Portable Bedside Monitor Capnograph/Pulse Oximeter • Capnostream [™] 35 Portable Respiratory Monitor		
Version 7.5 (Japan only) Version 8.5	Capnostream Software		
Smart CapnoLine H Plus Smart CapnoLine H CapnoLine H CapnoLine H 0 ₂ Smart CapnoLine Plus Smart CapnoLine O ₂ /CO ₂ Nasal FilterLine	etCO₂ Sampling Line for Microstream [™] –enabled capnography monitors		
OxiMax Max-A OxiMax Max-AL OxiMax MaxN MaxFast SoftCare	Nellcor™ SpO₂ Sensor		
	Additional Accessories Roll Stand Assembly Vesa mounting plate Manfrotto clamp Power Supply kit (Main Electrical Power Cord with AC adapter) Battery Pack Extra battery / charger 3.15 Amp Type F fuses FilterLine Starter Kit Sensor extension cables (4, 8, or 10 feet) SpO₂ Sensor Pack 		

Table 1. Medtronic Market-Released Devices and Accessory Components

7.1.1. Capnostream Monitor

The Capnostream monitor and its accessories provide continuous, non-invasive measurement and monitoring of:

- End-tidal carbon dioxide (etCO₂) level of carbon dioxide in exhaled breath.
- Respiratory rate (RR) breaths per minute.
- Fractional inspired carbon dioxide (FiCO₂) level of carbon dioxide present during inhalation.
- Peripheral oxygen saturation of arterial hemoglobin (SpO₂)
- Pulse rate (PR) pulsatile cycle in beats per minute via pulse oximeter technology

The device also provides an Integrated Pulmonary Index[™] (henceforth referred to as IPI) value, which is a numerical value that integrates four major parameters measured by Capnostream in order to provide a

Version 3.0, 29 Nov 2016

PRODIGY CIP

COVMOPO0560

simple indication of the patient's ventilatory status. The integrated parameters are etCO₂, RR, SpO₂, and PR. Only these four parameters are used to calculate IPI; other parameters are not taken into account.

Figure 1. Capnostream 20_p

Figure 2. Capnostream 35

7.1.2. End-tidal Carbon Dioxide (etCO₂) Sampling Line

A sample of the exhaled gases are delivered from the patient (via a cannula) into the monitor for $etCO_2$ measurement. The $etCO_2$ sample line (also referred to as a filter line) are a disposable single use sampling line.

Each study subject will be connected to the Capnostream monitor with an etCO2 sampling line.

Version 3.0, 29 Nov 2016

PRODIGY CIP

COVMOPO0560

Supplemental oxygen may also be delivered through the sampling line, as needed. Any supplemental oxygen would be delivered per usual clinical practice. The supplemental oxygen is not provided through the monitor.

Figure 3. etCO₂ Sampling Line

